1.4.1 Lymphedema Background

Patient-reported outcomes such as symptom assessment and QOL can serve multiple purposes, including acting as validation measures of treatment efficacy in the context of clinical trials and serving as reference points for clinical decision-making when modest differences in survival are anticipated among various treatment modalities [48-50]. It is possible in this trial that while the treatment outcomes with respect to disease recurrence are equivalent that the morbidity associated with each of the treatment arms is not the same. In this setting, it is critical that a comprehensive assessment of treatment-associated morbidity be performed in order to represent the entirety of the treatment experience. As the contemporary treatment for breast cancer evolves, it is important to examine the morbidity associated with various treatment regimens.

Arm Lymphedema: Arm lymphedema is one of the most dreaded complications of breast cancer treatments, in that it often causes physical discomfort, psychological distress, functional impairment, change in body habitus and self-image, chronic disability, and diminished QOL [51-55]. In addition, lymphedema incurs significant financial costs, both to the affected individual and to the national and international health care delivery systems. In a review of the published literature concerning breast cancer treatment-related lymphedema, Erikson et al. concluded “there is need for better understanding of the prevalence and morbidity of arm edema in population-based studies” [56]. As the contemporary treatment for breast cancer evolves, it is particularly important to examine the incidence of lymphedema and associated symptoms.

Of those treated for breast cancer, it has been reported that the incidence of lymphedema varies widely depending on the criteria applied [57]. The most common estimates reported are 20 to 40% for women undergoing axillary lymph node dissection [58-63]. The challenges related to lymphedema measurement, diagnosis, and follow-up are cited as the primary reasons for these large discrepancies in reported lymphedema incidence.

Armer et al. have reported that in a cohort of 211 breast cancer participants with 30 months post-treatment follow-up who were assessed using perometry, circumferences, and symptom assessment that the incidence of lymphedema ranged from 41 to 91% with 2 cm being the highest estimation method and symptoms the lowest [57, 64].

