In a recent report from the NSABP B-32 trial, arm volumes were assessed over 3 years following axillary lymph node dissection (n=1,975) or sentinel lymph node biopsy (n=2,006) using water displacement techniques. In this study, arm volume differences were only noted for 14% (compared to 8.6% at baseline) of patients undergoing axillary lymph node dissection and 7.5% (compared to 8.0% at baseline) of those undergoing sentinel lymph node biopsy. [65] Numbness and tingling were the two symptoms assessed in this study, as well as shoulder abduction. Radiation to the axilla was reported to increase the risk for residual arm volume difference (OR = 3.47) however the actual number of patients treated with XRT was very small (ALND Group: n = 22, 1.1% and SLND Group: n=13, 0.7%). While the reported incidence of lymphedema following sentinel node biopsy concurs with other studies, the reported incidence of limb volume differences following axillary dissection was lower than that reported in the majority of studies. Although this study provides some paired symptom data with objective measures of lymphedema, key symptoms of lymphedema (i.e. heaviness and swelling) were not included, and the very small number of patients treated with XRT demonstrates the gap in knowledge that we propose to address in the current trial.

Whether or not radiation treatment to the axillary lymph nodes or breast/chest wall increases the risk of developing lymphedema and/or associated symptoms is still unresolved. A number of studies have reported that there is no association. [60, 66]

It is even more unclear whether or not axillary XRT alone (or following sentinel lymph node biopsy) increases the risk of lymphedema. Therefore, in the setting of this proposed breast cancer treatment trial, it is imperative to obtain objective clinical assessment data and to use validated lymphedema symptom assessment tools to inform future decision-making related to these cancer

therapies. The clinical and patient-reported lymphedema assessments are more thoroughly described in [Section 10.5](#).

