7.1 Surgical Management

7.1.1 Mastectomy

Surgery may be completed as a total, simple, skin sparing, nipple sparing or modified radical mastectomy.

Margins should be negative, defined as no tumor on ink. A focally positive deep margin will be considered a negative margin if the deep margin is the pectoralis fascia and the pectoralis fascia was noted as removed in the operative description or pathology report. This is provided there is no evidence of pectoralis fascia invasion by imaging or pathological evaluation.

Lymph nodes must be evaluated by sentinel node biopsy or axillary dissection. The majority of these patients will have positive lymph nodes in order to qualify for enrollment. This protocol does not stipulate sentinel node versus axillary dissection, but does require lymph node management per standard of care. Patients will be recorded as having undergone a sentinel node only procedure or an axillary dissection. A sentinel node procedure will be considered an axillary dissection if more than 5 lymph nodes are removed.

Mastectomy and nodal evaluation must be completed within 56 days of the completion of neoadjuvant chemotherapy. Radiation must start per section 7.0.

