We will consider two different measures of arm lymphedema as secondary endpoints in this study. As a second measure of arm lymphedema, we will consider the percent change in ipsilateral arm volume post-radiation from its pre-radiation volume. The impact of lymphedema based on extent of surgery (sentinel vs. axillary dissection) has been reported elsewhere and therefore will not be focus of this study.

Breast Lymphedema: While upper extremity lymphedema is a recognized complication following axillary surgery for breast cancer, breast lymphedema can also occur and be associated with significant morbidity. To date, this condition has not been highlighted primarily because the objective measurement and diagnostic criteria have largely been unavailable. The most common criteria used are based on clinical signs of diffuse skin edema and erythema. Reconstructed breast edema will be captured in the CTCAE late morbidity reporting as well as in the cosmesis evaluation and the LBCQ questionnaire (Section 10.5.2).

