12.4.3 Lymphedema Assessment

Incidence of arm lymphedema by treatment arm: The proportions of patients with arm lymphedema (defined as a change of 10% or greater in ipsilateral arm volume from the pre-RT volume, see also Section 10.3.1 for definition of arm lymphedema) at 2 year post radiation will be summarized and will be compared across the two treatment arms using a two-sample test of proportions (Z test) with a two-sided alternative. Change in ipsilateral arm volume at each of the following time-points: 6, 12, 24 and 60 months post-radiation (relative to pre-RT) will be compared using a two sample t-test with a two-sided alternative. The changes in arm volume at these time points will also be analyzed as a repeated measure using a linear mixed model with patient as the random effect.

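### The 2-year arm-lymphedema comparison could be stratified by axillary surgery at no cost; the planned unadjusted test is valid, and the gain is small on the protocol's only head-to-head figures

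*Combined protocol and SAP*

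**What the plan says.** Section 12.4.3 sets out three analyses of arm lymphedema.

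- The 2-year proportions, with lymphedema "defined as a change of 10% or greater in ipsilateral arm volume from the pre-RT volume", "will be compared across the two treatment arms using a two-sample test of proportions (Z test) with a two-sided alternative".
- Change in arm volume at each time point "will be compared using a two sample t-test with a two-sided alternative".
- The volume changes are also "analyzed as a repeated measure using a linear mixed model with patient as the random effect". No fixed effects are listed.

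None of these names axillary surgery. Section 4.6 stratifies randomization only by type and timing of reconstruction.

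The factor will nevertheless be in the data. Section 7.1.1 states: "Patients will be recorded as having undergone a sentinel node only procedure or an axillary dissection". It also gives a rule: a sentinel procedure that removes more than 5 nodes counts as a dissection.

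On risk, Section 1.4.1 says: "The most common estimates reported are 20 to 40% for women undergoing axillary lymph node dissection". It then cites one large trial that compared the two operations and found arm-volume differences in 14% after dissection and "7.5% (compared to 8.0% at baseline) of those undergoing sentinel lymph node biopsy". The protocol remarks that the 14% is lower than most studies report.

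Section 10.5.1 says that the lymphedema effect "based on extent of surgery (sentinel vs. axillary dissection) has been reported elsewhere and therefore will not be focus of this study".

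**The concern.** The protocol's background describes a factor that is fixed by surgery before radiation, goes with the outcome, and is recorded anyway. The arm comparison does not use it. An unadjusted comparison then keeps the part of the outcome variance that the factor could remove. Any chance difference between arms in the share of dissected patients also passes into the estimated difference. The design does not balance this factor directly, because the stratification factors concern reconstruction only.

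Section 10.5.1 explains why the effect of surgical extent will not be studied. That is a different question from using it as a covariate when the two radiation schedules are compared.

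Reduced lymphedema is part of the second study hypothesis in Section 1.6. The plan also accepts the principle elsewhere: Section 12.3.2 adds a stratified sensitivity analysis for the primary endpoint, and Section 12.4.5 adjusts the utilization counts for imbalance left after randomization.

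**Working it through.** **The plan's own figure.** No sample size or power is given for lymphedema, so the only design figure to use is the 396 evaluable per arm in Section 12.2. With a 25% rate in both arms, a margin of 0.10, one-sided alpha 0.025 and 90% power:

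n = 2 × 0.25 × 0.75 × (1.960 + 1.282)² / 0.10² = 394.1, so 395 per arm against the stated 396. Also 792 / 0.90 = 880. Both reproduce.

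**Inputs.** N = 396 per arm. Sentinel risk pS = 7.5%. Dissection risk pA = 14% (same trial as the 7.5%), or 20% and 40% (the ends of the common range in Section 1.4.1, from other studies). The share dissected, q, is not in the documents. It is assumed to be 50%, range 30-70%.

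**Variance explained.** With p = q·pA + (1 − q)·pS,

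R² = q(1 − q)(pA − pS)² / [p(1 − p)].

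For 14% v 7.5% at q = 0.5: p = 0.1075 and p(1 − p) = 0.0959. The between-group part is 0.25 × 0.065² = 0.00106, so R² = 1.1%. The SE of the arm difference is √(2 × 0.0959 / 396) = 2.20 points. Removing the between-group part gives √(2 × 0.0949 / 396) = 2.19 points.

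For power, take a true difference that the crude test detects with 80% power, (1.960 + 0.842) × SE, and re-evaluate it with the smaller SE. The equivalent number of patients is 792 × [1/(1 − R²) − 1].

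| pA v pS (q = 50%) | R² (range for q = 30-70%) | SE, points | Equivalent patients | Power |
|---|---|---|---|---|
| 14% v 7.5% | 1.1% (0.8-1.1%) | 2.20 to 2.19 | about 9 | 80.0% to 80.4% |
| 20% v 7.5% | 3.3% (2.4-3.3%) | 2.45 to 2.41 | about 27 | 80% to 81.3% |
| 40% v 7.5% | 14.6% (10.5-15.5%) | 3.02 to 2.80 | about 135 | 80% to 85.8% |

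**Chance imbalance.** The between-arm difference in dissection share has SD √(2q(1 − q)/396), which is 3.26 points at q = 0.3 or 0.7 and 3.55 at q = 0.5. Multiplying by pA − pS gives the shift in the crude difference per SD of imbalance:

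- 14% v 7.5%: 0.065 × 3.26 to 3.55 = 0.21 to 0.23 points.
- 20% v 7.5%: 0.125 × 3.26 to 3.55 = 0.41 to 0.44 points.
- 40% v 7.5%: 0.325 × 3.26 to 3.55 = 1.06 to 1.15 points.

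The comparator is an SE of 2.20 to 3.02 points (q = 50%). At the 95% limit of imbalance (1.96 × 3.55 = 7.0 points) the shifts are 0.45, 0.87 and 2.26 points, or 0.21, 0.36 and 0.75 of the SE.

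**Error rate.** In 200,000 simulated trials per scenario with no arm effect (q = 50%), the planned Z test rejects in 4.9-5.1%. In the roughly 5% of trials with an imbalance of 7 points or more, it rejects in 5.4%, 6.7% and 12.9% for the three pairs. A Mantel-Haenszel test stratified by axillary surgery stays at 4.7-5.0% in those trials.

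**The case against.** The strongest reply is that nothing is wrong. A two-sample Z test after randomization is unbiased and holds its error rate, and its standard error already allows for chance imbalance in any factor. The objective in Section 2.4.1 is to estimate incidence by arm, which crude proportions do, and no power is claimed. This stands. A reader might infer that the planned result is biased or its error rate inflated. The documents do not support that: the overall simulated rate is about 5%, and the excess appears only among the minority of trials with a large imbalance.

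A second reply is that the risk contrast is uncertain here, and this also stands. A reader might take the 20-40% figures to make axillary surgery a main risk factor in this trial. Only 14% v 7.5% comes from one comparison. Setting 20-40% against 7.5% crosses studies, and Section 1.4.1 itself says that incidence depends heavily on the criteria used. Three features could also shrink the contrast:

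- Change is measured from a volume taken after surgery and before radiation, so early surgical swelling is already in the baseline.
- About 1% of patients in the cited trial had axillary radiation, whereas here nodal radiation is planned for all.
- The axillary field depends on the surgery (Sections 7.4 and 7.4.2): after a dissection only the undissected axilla is treated, and with fewer than 6 nodes removed the full axilla is included.

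A reader might also want to add body mass index, which Section 10.5 collects. Nothing in the documents ties it to lymphedema risk, so it is not recommended here.

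Two smaller replies hold in part. The mixed model lists no fixed effects, so it does not exclude adjustment, though it does not specify it either. Section 10.5.1 shows that surgical extent was considered, but it gives no reason against its use as a covariate.

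**Conclusion.** The point holds as an optional improvement of low priority. The planned comparison is valid but leaves a recorded, plausibly prognostic baseline factor unused.

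On the protocol's only head-to-head figures the gain is about 1% of variance, with 0.4 points of power. One SD of imbalance shifts the estimate by about 0.2 points against an SE of about 2.2. The gain would be material only if the contrast in this trial came near 40% v 7.5%: about 15% of variance, and 80% to 85.8% power. It could also be smaller than the head-to-head pair suggests.

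These sizes assume a dissection share of 30-70%, a 2-year arm measurement for all 396 per arm (fewer would widen every SE), and allocation that behaves like simple randomization with respect to axillary surgery.

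**What to change.** In Section 12.4.3, make the main comparison of the 2-year proportions a risk difference stratified by axillary surgery (sentinel node only v dissection, by the Section 7.1.1 rule), either Mantel-Haenszel or standardised from a logistic model. Add the same term to the arm-volume mixed model. Keep the crude Z test as a sensitivity analysis.

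Define the covariate as status at randomization. Section 7.0 counts later lymph node removal within the initial surgery and the trial is un-blinded, so nodal surgery after allocation should not enter the covariate.

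The cost is SAP wording, with no new data. Writing it in before the results are seen avoids a post hoc choice if the arms turn out unbalanced.

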5.0 STUDY CALENDAR

The pre-study testing intervals are guidelines only. Laboratory and clinical parameters during treatment are to be followed using individual institutional guidelines and the best clinical judgment of the responsible physician. It is expected that patients on this study will be cared for by physicians experienced in the treatment and supportive care of patients on this trial.

Pre-Study Testing Intervals

- To be completed ≤ 7 DAYS before registration: Pregnancy test,
- To be completed ≤ 28 DAYS before registration: history and physical.

	Prior to Registration	Before RT [¥]	At completion of RT [€]	2 to 8 weeks post RT	6, 12, 18 mos. post RT*	2 years post RT*	30 mos., 3,4 and 5 years post RT**	10 and 15 years post RT***
Tests & Observations								
H&P, Weight, PS	X	X (1)	X	X	X	X	X	
Height	X							
Mastectomy or reconstruction complications		X	X	X	X	X	X	
Recurrence (scan or clinical) Assessment					X	X	X	X
Adverse Events Assessment		A	A	A	A	A	A	
Clinical Lymphedema Assessment		B	B	B	B	B	B	
Cardiac and Brachial Plexopathy Events					C	C	C	C
Arm Circum. Measure (see §10.5)		X			X (2)	X		
Photographs for Cosmetic Assessment		D				X (4)		
Laboratory Studies								
Serum or Urine HCG	E							
Hemoglobin A1C	F							
Questionnaires								
Breast-Q Post-mastectomy		G						
Breast-Q Post-reconstruction		G				X	X (3)	
LBCQ		X			X (2)	X	X (3)	
BLE		H			X (2)	X	X (3)	
Economic Surveys		I	J	I	J			
EQ-5D-3L		X			X	X		
Was It Worth It Questionnaire						X		
Correlative Study (optional)	To be collected at baseline, see Sections 6.2 and 13.1							
Whole Blood								

¥ May be completed at any time following patient consent (before or after registration, but prior to treatment)

€ May be completed within 72 hours of last radiation treatment.

* +/- 6 weeks.

** For 30-month visit, +/- 6 weeks; for 3, 4, and 5-year visits, +/- 3 months

*** +/- 6 months. All follow up, including survival status, done after 5 years will be gathered by record review only.

A Assessment of side effects related to radiation therapy should be assessed according to the history and physical examination.

B To be assessed per the CTCAE criteria.

C Will be assessed by medical record review.

D Only for patients with final reconstruction completed before radiation.

E For women of childbearing potential. Must be done within 7 days prior to registration.

F For diabetic patients only, to be done ≤ 90 days before registration.

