G Breast Q Post Mastectomy questionnaire; unless already reconstructed, then Breast-Q Post Reconstruction.

H Only for patients who have had reconstruction

I Prior to RT, patients will be given the Patient Health Care Diary and the Health Care Expense Questionnaire (Appendix VII) to be returned to the clinic at the 2 to 8 week visit (see Section 10.7).

J After completion of RT, the patient will be given the Patient Health Care Utilization Diary (Appendix VIII) and will be asked to return it at the 12-month visit (see Section 10.7).

1 Need not be repeated if done within the past 30 days

2 To be completed at 6 months only. (up to 18 months, whenever reconstruction is completed, for BLE)

3 To be completed at 5 years only.

4 +/- 2 months

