10.5 Lymphedema

Lymphedema assessments (i.e., bilateral arm circumference measurements) will be administered before radiation, 6 months after radiation and then again at 2 years after completion of radiation therapy. Body mass index (BMI) will also be ascertained. Lymphedema questionnaires will be completed as described in Section 10.5.2. Patients who develop a new or recurrent breast cancer will discontinue the arm lymphedema assessments.

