10.5.1 Clinical Assessment

All planned lymphedema evaluations will include clinical assessment for signs and symptoms of lymphedema. Any patient complaining of “arm swelling” or “heaviness” or showing signs of extremity swelling (≥ 2 cm difference between upper extremities at any measurement point) will be treated according to current practice guidelines and referred to a lymphedema health care provider. In addition, patients will be instructed to call their oncologist if they develop any new arm symptoms during the periods between planned assessments. Such patients will be scheduled for immediate evaluation and arm measurements.

Arm Measurement: Circumferential measurement of limb volume will be performed on both affected and non-affected arms. Patients will sit with the arms resting horizontally palms-down on a bedside table placed at a level slightly below the axilla. The patients will be instructed to wear loose sleeves or short sleeves/sleeveless tops and to remove any arm jewelry prior to the measurement. Measurements will be taken at the wrist, half way between the wrist and antecubital fossa (below the elbow), at the antecubital fossa, half way between the antecubital fossa and the axilla, and at the axilla. In all cases, the plane of the tape around the arm will be held perpendicular to the long axis of the arm and perpendicular to the floor. The tape will be held snugly around the body part without indenting the skin or compressing subcutaneous adipose tissue. If gaps between the skin and tape are seen in some individuals, tension should not be increased to reduce the gap. Arm measurements and other required data will be recorded on the Arm circumference measurement case report form (Appendix IV) which is to be completed by the local study coordinator. The standard formula (based on cylindrical slices) will be utilized in this study to calculate volume (V) from circumference (U) measures.

PowerPoint slides located on the A221505 study page will provide instructions on how to perform these measurements. The procedures used in CALGB 70305 will be followed in this study.

Arm Lymphedema: A patient will be considered to have mild lymphedema if she has symptomatic arm swelling or heaviness with less than a 10% increase in volume of the ipsilateral arm from pre-radiation volume.

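### Section 12.4.3 plans arm-volume comparisons at 12 and 60 months with no scheduled measurements, and its lymphedema definition lacks a direction, a correct cross-reference and any use of the contralateral arm

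*Combined protocol and SAP*

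**What the plan says.** Section 12.4.3 has three arm-volume analyses. The first compares, at 2 years, the proportion of patients whose ipsilateral arm volume has changed by at least 10% from its pre-radiation value. The second is a set of two-sample t-tests: "Change in ipsilateral arm volume at each of the following time-points: 6, 12, 24 and 60 months post-radiation (relative to pre-RT". The third covers the same visits: "The changes in arm volume at these time points will also be analyzed as a repeated measure using a linear mixed model". For the definition of arm lymphedema the section sends the reader to Section 10.3.1.

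On collection, Section 10.5 says that the arm circumference measurements "will be administered before radiation, 6 months after radiation and then again at 2 years after completion of radiation therapy". The calendar row "Arm Circum. Measure (see §10.5" is marked before radiation, in the shared 6/12/18-month column with footnote 2, and at 2 years. It is blank in the column that runs from 30 months to 5 years. Footnote 2 reads "To be completed at 6 months only. (up to 18 months, whenever reconstruction is completed, for BLE", so its extension to 18 months concerns the breast lymphedema (BLE) survey and not the tape measurement. The Appendix IV form offers three reporting periods: before radiation, 6 months and 24 months.

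On method, Section 10.5.1 says "Circumferential measurement of limb volume will be performed on both affected and non-affected arms". Section 10.5 also collects body mass index. Neither the contralateral arm nor body size enters the analyses in Section 12.4.3.

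**The concern.** Estimating arm lymphedema by treatment arm is a stated objective (2.4.1), and reduced lymphedema is one of the study hypotheses (1.6). Three things in the analysis text get in the way.

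- Half of the named post-radiation visits have no scheduled arm volume behind them. As written, two of the t-tests cannot be run, and the mixed model calls for visits that do not exist.
- The event rule gives no direction, and it refers to a section on another subject. Two analysts could code the endpoint differently.
- An arm compared only with its own earlier volume cannot separate swelling from a general change in arm size, for example after weight gain or loss over two years. The data needed to separate them are collected and left unused.

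At stake are the completeness and the interpretability of a secondary endpoint. The primary endpoint and the sample size do not depend on it.

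**Working it through.** **1. Visits analysed against visits measured.**

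| Source | Before RT | 6 mo | 12 mo | 24 mo | 60 mo |
|---|---|---|---|---|---|
| Analysis, Section 12.4.3 | reference | yes | yes | yes | yes |
| Section 10.5 | yes | yes | no | yes | no |
| Calendar row with footnote 2 | yes | yes | no | yes | no |
| Appendix IV form | yes | yes | no | yes | no |

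The three collection sources agree with one another, and the analysis section is the outlier. Planned {6, 12, 24, 60} less scheduled {6, 24} leaves {12, 60}: 2 of 4 visits. At 5 years the calendar has CTCAE grading and questionnaires, neither of which yields a volume.

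**2. The definition.** Section 12.4.3 speaks of a change of at least 10%. Section 10.5.1 describes mild lymphedema as symptoms with an increase below 10% from the pre-radiation volume, which implies that the threshold is an increase. Section 10.5.1 defines only this mild category, so the 10%-or-more rule stands in 12.4.3 alone. Section 10.3.1, the place cited, is Local Recurrence.

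**3. How far the ipsilateral-only rule could misclassify.** The documents give no rate, standard deviation or power for this endpoint, so there is no stated figure to reproduce, and every input in steps 3 and 4 except the 396 per arm is an assumption. Take a patient without lymphedema. Let the general (systemic) change in arm volume have mean m% and SD s%, shared equally by both arms, and let each arm's percentage change carry independent measurement error with SD e%.

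- Ipsilateral-only rule: P(change ≥ +10%) = 1 − Φ((10 − m)/√(s² + e²)).
- Contralateral change subtracted, which approximates the ratio for small changes: P = 1 − Φ(10/(√2·e)).

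| s | m | e | Ipsilateral only | Contralateral subtracted |
|---|---|---|---|---|
| 3 | 0 | 2 | 0.3% | 0.02% |
| 3 | 0 | 3 | 0.9% | 0.9% |
| 5 | 0 | 3 | 4.3% | 0.9% |
| 5 | 3 | 3 | 11.5% | 0.9% |
| 7 | 0 | 3 | 9.5% | 0.9% |
| 7 | 3 | 3 | 17.9% | 0.9% |

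Over s = 3 to 7, m = 0 to 3 and e = 2 to 3, the ipsilateral-only rule flags about 0.3% to 18% of unaffected patients, against about 0.02% to 0.9% after correction. With m = 0 an equal share falls to −10% or below, so the undirected wording doubles the first figure.

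**4. Consequence for the comparison.** If a false-positive rate f is the same in both groups, a true rate p is observed as p + (1 − p)f, and the difference shrinks by the factor (1 − f). With assumed true rates of 20% and 12%, the 396 evaluable patients per arm of Section 12.2, and a two-sided 5% test:

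| f | Observed rates | Difference | Power |
|---|---|---|---|
| 0 | 20.0% vs 12.0% | 8.0 points | 87% |
| 2% | 21.6% vs 13.8% | 7.84 points | 83% |
| 5% | 24.0% vs 16.4% | 7.6 points | 76% |
| 10% | 28.0% vs 20.8% | 7.2 points | 66% |

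**The case against.** The strongest reply is that little is lost. Objective 2.4.1 rests on the 2-year proportion, and arm volume is scheduled at 24 months. The 6- and 24-month t-tests and a mixed model on those two visits can still be run. CTCAE lymphedema grading continues at clinic visits to 5 years, and the LBCQ symptom questionnaire is given at 6 months, 2 years and 5 years. All of this stands, and a reader who infers that the lymphedema objective cannot be met goes too far.

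Nor is it right to say that arm volume is never measured at other times. Section 10.5.1 says of patients who report new arm symptoms between planned assessments: "Such patients will be scheduled for immediate evaluation and arm measurements". Those patients are selected by their symptoms, however, and the form has no reporting period for them. They cannot supply a randomised comparison at 12 or 60 months.

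The undirected wording is partly answered by Section 10.5.1, and one word repairs it.

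On the contralateral arm, change from the arm's own pre-radiation volume is a deliberate choice, used consistently in Sections 10.5.1 and 12.4.3. A ratio adds the second arm's measurement error. The contralateral arm is not always a clean control either: contralateral DCIS is eligible (3.2.5), and contralateral mastectomy is anticipated (7.4.1, 7.4.3). These points stand. They argue for adding the ratio as a pre-specified analysis with a rule for such patients, and against replacing the endpoint outright.

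A reader might also infer that weight-related false positives are as common as true lymphedema, by comparing the range above with the 3% to 9% figures in Section 1.2. The documents do not support that. The spread of weight-related arm change is assumed, at the mildest settings the misclassification is below 1%, and Section 1.4.1 also cites 14% and 7.5% from a surgical trial and 20% to 40% after axillary dissection.

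**Conclusion.** The schedule mismatch is certain: 2 of the 4 planned post-radiation arm-volume visits, 12 and 60 months, have no scheduled measurement. The missing direction and the wrong cross-reference are equally plain from the text.

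The contralateral point holds in a limited form. Both arms are measured and only one is used, so a general change in arm size can be counted as lymphedema or can conceal it. The frequency cannot be determined from the documents. The 0.3% to 18% range and the power figures only illustrate what the assumed inputs would imply, and they also assume that general change moves both arms equally.

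It might be inferred that the ipsilateral-only rule favours one treatment. Randomisation gives no reason to expect that. Misclassification should be similar in the two groups, so it would distort the incidence estimates and dilute a difference in either direction. The point concerns a secondary endpoint and should be corrected before the analysis.

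**What to change.** In Section 12.4.3:

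- Restrict the arm-volume t-tests and the mixed model to 6 and 24 months.
- Define arm lymphedema at 2 years as an increase of 10% or more in ipsilateral arm volume from the pre-radiation value.
- Correct the cross-reference to Section 10.5.1, and state the same 10% rule there, since that section now defines only the mild category.
- Add a pre-specified analysis of the baseline-corrected ratio: (ipsilateral/contralateral volume at follow-up) ÷ (ipsilateral/contralateral volume before radiation) − 1, with 0.10 or more as the event, and the same quantity analysed as continuous.
- State how patients with contralateral breast or axillary surgery are handled in the ratio analysis, for example by excluding them from it and reporting their number by arm.
- Do not adjust the treatment comparison for change in BMI. It is measured after randomisation, so conditioning on it can bias the comparison, and the ratio already removes most shared change.

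The cost is analysis-plan wording, because both arms are already recorded on the Appendix IV form. The small downsides are the second arm's measurement error and the patients whose contralateral arm is not normal. Adding 12- and 60-month measurements instead would need a calendar and form change, and could not recover visits that have already passed.
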